5.4. Prior and Concomitant Medications

Concomitant, non-cancer medications will be summarized for the FAS population. Prior medications will be presented in a data listing.

Concomitant medications are those protocol-permitted medications that were given during the time interval from the first dose of any study drug to the end of the last cycle. Medications collected through electronic case report forms (eCRFs) will be coded to Anatomical Therapeutic Classification (ATC) and PT, where applicable, using the most recent World Health Organization Drug Dictionary (WHO-DD) version WHODrug-Global-B3 202309.

Concomitant medications will be summarized by ATC and PT and presented in a descending order of frequency for ATC and PT within an ATC based on the overall group. If a patient took multiple medications within the same ATC, the patient will only be counted once for that ATC.

Similar logic applies to PT summaries. The number and percentage of patients receiving any concomitant medications will be summarized overall.

Handling of Missing Start and/or End Date for Medications Entered into EDC

Medications with incomplete start and/or end dates will be imputed according to the specifications described below. Those with incomplete start and/or end dates will be assumed to be concomitant if it cannot be shown that the medication was not taken outside of the treatment period.

For completely missing or partially missing start dates:

- If the start date has month and year but day is missing, the first dose date of any study drug will be used if the month and year is the same as the first dose date of any study drug, otherwise, the first day of the month will be used.
- If the start date has year, but day and month are missing, then the first dose date of any study drug will be used if the year is the same as the first dose date of any study drug, otherwise January 1st will be used.
- If the start date is completely missing, then it will be imputed as the first dose date of any study drug.

After the imputation, the imputed start date will be compared with corresponding stop date, if available. If the imputed start date is later than the stop date, the start date will be imputed with the stop date instead.

For completely missing or partially missing stop dates for concomitant medications that are not ongoing at the time of data cutoff:

- If the stop date has month and year but day is missing, the last day of the month will be used.
- If the stop date has year, but day and month are missing, December 31st will be used.
- If the stop date is completely missing, the last dose date of any study drug will be used.

After the imputation, the imputed stop date will be compared against the death date for patients who died. If the date is later than the death date, the date of death will be used to impute the stop date instead.

Prior and concomitant medications will be listed with an indicator for prior or concomitant.

5.5. Summary of Protocol Deviations

5.5.1. Definitions and Process for Identifying Protocol Deviations

Protocol deviation refers to situations where a patient's eligibility for study entry or a specific data collection deviate from the entry criteria or study procedure as specified in the protocol. Protocol deviation cases at the patient level with specific data elements of concern need to be summarized and reported in the CSR. Protocol deviations will be categorized as major or minor. Major protocol deviations are those that could affect the integrity of the data or adversely affect

patients' safety. Criteria that define major or minor protocol deviations will be specified, documented, and signed off on prior to study database lock. Specifically, a protocol deviation specifications document that describes the criteria defining major and minor protocol deviations, the categories of major protocol deviations, and the list of patients who had at least one protocol deviation case with the classification of major or minor will be created and signed off prior to study database lock.

5.5.2. Summary of Protocol Deviations

A protocol deviation summary will be generated for the final analysis.

The number and percentage of patients in the FAS population with protocol deviations will be tabulated for each of the following categories.

- Patients with at least one protocol deviation (major or minor)
- Patients with at least one major protocol deviation
- Patients with at least one protocol deviation in each of the major deviation categories

Protocol deviations will be listed with details and flags indicating major or minor for the FAS population.

G1 Therapeutics

6. CLASSIFICATION OF PRIOR, CONCOMITANT, AND SUBSEQUENT ANTICANCER THERAPIES

Prior therapies refer to those anticancer treatments that patients received prior to the first dose date of any study drug, including radiotherapies, surgical procedures, and systemic anticancer therapies.

Concomitant therapies refer to those treatments, other than study drugs, that could be utilized concurrently with study drug(s) as specified in the protocol. That is, the therapies that were given in the time interval from the first dose of any study drug to the end of the last cycle

Subsequent therapies refer to anticancer treatments received following investigational study drug discontinuation while the patient was still in the study (i.e., in the Survival Follow-up period).

The rules of imputation of missing onset or stop dates for medications described in Section 5.4 are, in general, applicable for missing onset or stop dates imputation for anticancer therapies in any format (radiotherapies, surgical procedures, or systemic anticancer therapies).

6.1. **Prior Anticancer Therapies**

Summaries of prior anticancer therapieswill be generated for the final analysis based on the FAS population. Prior therapies in the adjuvant context will be excluded from the analysis in this section.

The number and percentage of patients with any prior anticancer therapies will be summarized for the FAS population. The number and percentage of patients with any prior radiotherapies, any prior surgical procedures that were related to breast cancer, and any prior systemic anticancer therapies will also be summarized. Prior systemic anticancer therapies will then be further summarized based on ATC and PT and presented in a descending order of frequency for ATC and PT withing an ATC based on the overall group.

Data listings will be produced for all prior anticancer therapies, including detailed information related to prior systemic anticancer therapies such as setting, regimen, start/stop dates, and detailed information related to prior surgical procedures and radiotherapies for the FAS population.

6.2. Concomitant Anticancer Therapies

Summaries for concomitant anticancer therapies will be generated for the FAS population at the final analysis.

The number and percentage of patients receiving any concomitant anticancer surgical procedures or radiotherapies that were related to disease under study will be summarized..

Detailed information for concomitant surgical procedures and radiotherapies will be included in the data listing for the FAS population.

6.3. Subsequent Systemic Anticancer Therapies

Subsequent anticancer treatments (SACT) will be summarized for the FAS population at the final analysis.

The number and percentage of patients receiving at least one SACT in any modality (systemic anticancer therapies, surgical procedure, or radiotherapy) as well as for each of the modalities will be summarized.

In addition, for the subsequent systemic anticancer therapies, the total number of lines of therapy will be summarized both descriptively and categorically. The number of patients who had at least one dose of any systemic anticancer therapies will be the denominator for percentage calculation..

Furthermore, the number and percentage of patients with any subsequent systemic anticancer therapies will be summarized based on ATC and PT and presented in a descending order of frequency for ATC and PT within an ATC. The best overall response to each subsequent line of therapy and disease progression status as collected will be presented in data listings.

Handling of Missing Start Date for SACT

SACTs with incomplete start dates will be imputed for the purpose of censoring ORR, CBR, DOR, and PFS, due to start of SACTs. The rules of imputations are described below.

For completely missing or partially missing start dates:

- If the start date has month and year but day is missing, the date of discontinuation of last study drug will be used if the month and year is the same as the date of discontinuation of last study drug, otherwise, the first day of the month will be used.
- If the start date has year, but day and month are missing, then the date of discontinuation of last study drug will be used if the year is the same as the date of discontinuation of last study drug, otherwise January 1st will be used.
- If the start date is completely missing, then it will be imputed as the date of discontinuation of last study drug.

Corresponding data listings will be provided for the FAS population.

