# 11.7. Survival Follow-up Phase

After completion of the Safety Follow-up Visit, the patient will be followed approximately every 3 months for survival. Survival Follow-up Visits can be via telephone, email, or clinic visits.

Information will be collected until the end of the study (or death) to record the patient's status (alive or dead). In addition, details of any subsequent systemic anti-cancer therapy initiated, including name(s) of agent(s), dates (start/stop) administered, best response to the treatment, and date of progression should also be reported to the best of their ability.

G1T28-213

If a patient withdraws consent for further study procedures, the site should clarify if the patient (or legally authorized representative where allowed by local regulation) remains open to survival contact and associated data collection. Provided that the patient has not withdrawn consent for follow up contact, information from medical records may be substituted for phone or other contact, provided that records are available as source documentation. Public records may be used to verify survival status if permitted by institutional or country guidances.

G1T28-213

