8.1. Definitions of Efficacy Endpoints

8.1.1. Primary Efficacy Endpoints – Progression Free Survival

Progressive disease (PD) and tumor response status are programmatically determined according to RECIST v1.1 based on the radiographic tumor assessment data recorded on the eCRF by the Investigator for target lesions, the investigator assessment of non-target lesions, and the status of new lesions. For a patient, the status of PD will be determined using all radiographic tumor scan data assessed prior to or on the date of the data cutoff to conduct the analysis for PFS. In the situation where PD and withdrawal of consent or PD and initiation of subsequent anticancer therapy occurred on the same day for a patient, the PD status will be assumed for that patient.

Radiographic PD and death due to any cause during the study are referred to as PFS events.

PFS is defined as the time (months) from date of C1D1 to the date of the first documented disease progression, or death in the absence of PD for those who had a PFS event, and the time from date of C1D1 to the censoring date for those who did not have a PFS event. Specifically, PFS is calculated as (date of PFS event or censoring – date of C1D1+ 1)/ 30.4375. The analysis for PFS will be based on the FAS.

Details for PFS calculation and censoring rules can be found in Table 6.

Situation	Date of Event or Censoring	Outcome
Disease progression per RECIST Version 1.1	Date of the first documented progression	PFS event
Death without a PD	Date of death	PFS event
Incomplete or no baseline tumor assessments	Date of C1D1	Censored
No progression	Date of the last adequate radiological tumor assessment with no documented disease progression	Censored
Treatment discontinuation for reasons other than disease progression	Date of the last adequate radiological tumor assessment with no documented progression	Censored
Subsequent anticancer treatment started prior to documented disease progression	Date of last adequate radiologic assessment prior to or the date of initiation of subsequent anticancer treatment	Censored

Table 6PFS Calculation and Censoring Rules

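### Incomplete start dates of subsequent anticancer treatment are imputed to the earliest possible date with no check against progression, so a PD documented after drug discontinuation can be censored

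*SAP*

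**What the plan says.** SAP 6.3 states why the dates are imputed: "SACTs with incomplete start dates will be imputed for the purpose of censoring ORR, CBR, DOR, and PFS, due to start of SACTs". There are three rules.

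- Day missing: the drug-discontinuation date if it falls in the same month and year; "otherwise, the first day of the month will be used".
- Day and month missing: the drug-discontinuation date "if the year is the same as the date of discontinuation of last study drug, otherwise January 1st will be used".
- All missing: "If the start date is completely missing, then it will be imputed as the date of discontinuation of last study drug".

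SAP section 6 places SACT after the study drug: "Subsequent therapies refer to anticancer treatments received following investigational study drug discontinuation while the patient was still in the study". Each rule therefore picks the earliest admissible date.

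SAP Table 6 has a row for "Subsequent anticancer treatment started prior to documented disease progression". Its outcome is censored, at the last adequate scan up to the SACT start. SAP 8.1.2 applies the same censoring rules to DOR. The one safeguard is in SAP 8.1.1: if PD and SACT start fall on the same day, the patient counts as progressed.

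**The concern.** An imputed SACT date that lands before a documented PD removes that PD from the primary endpoint and replaces it with an earlier censored time. The censoring is informative, because new treatment usually follows progression. For PFS and DOR events it can only favour the drug, and a single-arm trial read against a historical median of 5.6 months has no control arm in which the same error would occur.

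The route is built into the plan. Treatment may stop for toxicity or clinical progression before radiographic PD. Protocol 10.1 then continues scans every 12 weeks, and Protocol 17.4 asks sites to document objective progression even after treatment has stopped. Incomplete SACT dates are plausible: Protocol 11.7 collects follow-up by telephone, email or clinic visit, and says of the SACT details that these, up to the "date of progression should also be reported to the best of their ability".

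The SAP makes comparable checks elsewhere. Imputed medication and adverse-event start dates are compared with stop dates, and imputed stop dates with death (SAP 5.4 and 9.2.2). SACT dates, which feed the primary endpoint, have no such check.

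**Working it through.** **The plan's own figures, for context.** SAP 1.3 gives 45 patients, 10 months' accrual, 14 months' follow-up and exponential PFS. Expected events = N × [1 − (e^(−14λ) − e^(−24λ)) / (10λ)]. For HR 0.70, λ = ln 2 / 8.0 = 0.0866, so 45 × [1 − (0.2973 − 0.1250)/0.866] = 36.05. For HR 0.80, λ = 0.0990 gives 37.9. One-sample log-rank power at one-sided 0.1 is 79.5% and 53.6%. The stated 36 and 38 events, 80% and 54%, reproduce. The point below does not rest on them.

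**The rule on dated cases.** The SAP 6.3 rules, Table 6 and the same-day rule were applied to constructed dates:

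| Drug stopped | PD | True SACT | Day missing | Day and month missing | All missing |
|---|---|---|---|---|---|
| 6 Jun 2022 | 18 Jul | 25 Jul | 1 Jul: censored | 6 Jun: censored | 6 Jun: censored |
| 18 Jul 2022 | 18 Jul | 25 Jul | 18 Jul: event | 18 Jul: event | 18 Jul: event |
| 18 Jul 2022 | 15 Jul | 25 Jul | 18 Jul: event | 18 Jul: event | 18 Jul: event |
| 12 Dec 2022 | 23 Jan 2023 | 6 Feb 2023 | 1 Feb: event | 1 Jan: censored | 12 Dec: censored |
| 5 Jul 2022 (last dose) | 18 Jul | 25 Jul | 5 Jul: censored | 5 Jul: censored | 5 Jul: censored |

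In every row the true order is PD, then SACT. An event is lost only when PD comes after the discontinuation date. Rows 2 and 3 show the protection: the imputed date never precedes discontinuation, and ties go to PD. Row 4 shows that a missing day alone does not always do harm.

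Row 5 shows why the undefined term matters. Doses fall on Days 1 and 8 of a 21-day cycle and scans at 6- or 9-week intervals, so a scheduled scan falls near Day 1 of a cycle, about two weeks after the previous Day 8 dose. If discontinuation means last dose, a patient who progresses on treatment usually has PD after it.

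**Size.** The documents give neither the share of incomplete dates (m) nor the share of progressors who stop before PD (d). Assumed ranges: m 5-30%, d 10-50%. Roughly, events lost = E × d × m, with d = 1 on the last-dose reading. A simulation (30 patients, true median 5.6 months, protocol scan schedule, administrative censoring uniform on 14 to 24 months, 1,500 runs per setting) gave E = 26.52 events without the imputation error and these mean losses:

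| | m = 5% | 10% | 20% | 30% |
|---|---|---|---|---|
| Decision date, d = 10% | 0.12 | 0.23 | 0.51 | 0.78 |
| Decision date, d = 30% | 0.38 | 0.78 | 1.57 | 2.41 |
| Decision date, d = 50% | 0.65 | 1.32 | 2.67 | 4.05 |
| Last dose | 1.29 | 2.61 | 5.29 | 8.04 |

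For comparison, 26.52 × 0.30 × 0.10 = 0.80. The product treats every incomplete date in an exposed patient as harmful, which row 4 above shows is an upper view when only the day is missing. The mean upward shift in the Kaplan-Meier median is 0.01 to 0.74 months over the decision-date rows and 0.24 to 2.5 months over the last-dose row.

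**The case against.** The strongest reply is that the typical progressor is safe. Treatment runs until progression, so a patient who stops because of PD has PD on or before the decision to stop, and the event is kept. This stands. A reader might infer that any PD sharing a month with a partly dated SACT is lost; the documents do not support that. The first of the month is used only if the drug was stopped in an earlier month. The wider exposure depends on the last-dose reading, and the SAP says last dose date where it means that (5.4, 9.2.2) but uses a different term in 6.3.

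A reader might also infer that the rule favours the drug throughout. It does not. SAP 8.1.2 uses the SACT date to cut off scans for response, so for ORR and CBR an early date can only drop scans, and an earliest-date rule is a recognisable conservative choice there. The favourable bias is confined to PFS and DOR.

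On size, if one randomly chosen PD is turned into a censored time, the hazard falls by about 3%, but the Kaplan-Meier median is unchanged in 89% of simulated runs; its 95% interval averages about 6.5 months wide. SAP 8.2.2 is descriptive, with no test to tip.

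Imputed values are flagged in listings (SAP 4.2) and censoring reasons are listed (8.2.2), so with 30 patients a case could be traced. Tracing it does not restore the event to the estimate.

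Finally, Table 6 also censors patients who stop treatment for reasons other than progression. If that row overrode a later PD, some exposed patients would be censored anyway. But SAP 8.1.1 determines PD from all scans up to the cutoff, so a later PD is more naturally read as an event.

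**Conclusion.** The rule as written gives a wrong result in a definable group: patients whose PD is documented after the discontinuation date and whose SACT start date is incomplete. In them a true PFS or DOR event can become an earlier, informatively censored time. Nothing in the SAP prevents this, and no PFS sensitivity analysis would reveal it.

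The size cannot be fixed from the documents. With 5-10% incomplete dates on the decision-date reading, the loss is about one event or fewer of 30 patients (at most 1.3, when half of progressors stop before PD), which is likely minor. On the last-dose reading it is 1.3 to 2.6 events at the same rates, and up to 8.0 at 30%. These figures rest on the assumed ranges, exponential PFS with a 5.6-month median, and 14 to 24 months of follow-up. The documents do not show that the primary result is materially inflated; they show an avoidable error in one direction for PFS and DOR. It should be corrected.

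**What to change.** In SAP 6.3:

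1. Define the drug-discontinuation date (decision date or last dose) and keep it as the lower bound for any imputed SACT date.
2. Add that, for PFS and DOR, an imputed SACT date may not precede a documented PD when the known date parts allow PD to come first. In that case set it to the PD date, so that the same-day rule in 8.1.1 keeps the event. In the first dated case all three patterns become 18 July and the event stays. A SACT recorded as June with PD on 18 July would still be censored, because the known parts put SACT first.
3. Flag in the PFS and DOR listings each imputation that changes an outcome.
4. Add a PFS sensitivity analysis without SACT censoring.

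The cost is a few SAP sentences, a small programming change and one extra table. The downside is that a patient who truly began SACT shortly before PD, with an incomplete date, would count as an event. This should be rare, because Protocol 10.1 and 11.2.1 end tumor assessments when subsequent therapy starts, so a documented PD normally comes first.

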7. STUDY DRUG EXPOSURE, DOSE INTENSITY AND MODIFICATION

Analyses described in this section will be based on the safety population unless otherwise specified.

7.1. Duration of Study Drug Exposure

Duration of study drug exposure (weeks) is defined as the duration from Day 1 of Cycle 1 to the End of cycle for the last cycle. That is, duration of drug exposure (weeks) = (End of cycle for the last cycle in the study – Day 1 of Cycle 1 + 1)/7, where the definitions for End of cycle for the last cycle and Day 1 of Cycle 1 are provided in Table 3.

The duration of study drug exposure will be summarized at the final analysis. The total number of cycles that a patient received will be summarized as a continuous variable, as well as a categorical variable. That is, descriptive summary statistics will be provided for the total number of cycles that patients received, and the number and percentage of patients that received exactly 0, 1, 2..., to the maximum number of cycles will also be summarized.

Corresponding data listings will be provided.

7.2. Cumulative Dose and Dose Intensity

Dose administration parameters will be summarized at the final analysis.

The definitions for cumulative delivered dose, delivered dose intensity, relative cumulative dose, and relative dose intensity at the patient level, along with other parameters involved in the calculation of these variables are presented in Table 4. All collected dose information will be used in the calculation.

The calculated cumulative delivered dose, delivered dose intensity, relative cumulative dose, and relative dose intensity will be summarized as continuous variables.

All variables described in Table 4 will be included in the data listing except for the study drug administration schedule.

G1 Therapeutics

Parameter	Meaning	Trilaciclib	Sacituzumab govitecan-hziy
Study drug administration schedule	Drug dose and schedule per protocol	240 mg/m ² IV on Day 1 and Day 8 of a 21-day cycle	10 mg/kg IV administered on Day 1 and Day 8 of each 21-day cycle.
Cumulative delivered dose [Unit]	Sum of doses over the duration of the study drug administration	Sum of doses over the duration of trilaciclib administration [mg/m ²]*	Sum of doses over the duration of sacituzumab govitecan-hziy administration [mg/kg]
Delivered Dose Intensity [Unit]	Cumulative dose administered per week	Cumulative dose (mg/m ²) / duration of study drug exposure in weeks [(mg/m ² /week)]	Cumulative dose (mg/kg) / duration of study drug exposure in weeks [(mg/kg/week)]
Relative cumulative dose (%)	Cumulative delivered dose over cumulative prescribed dose	[Cumulative delivered dose (mg/m ²) / (240 × 2 × number of cycles) (mg/m ²)]*100	[Cumulative delivered dose (mg/kg) / (10 × 2 × number of cycles) (mg/kg)]*100
Relative dose intensity (%)	Delivered dose intensity over prescribed dose intensity	[Delivered dose intensity/(480/3)]*100	[Delivered dose intensity/20/3]*100

Table 4Dose Administration Parameters for Study G1T28-213

* Actual doses administered were collected in unit of mg on the eCRF. For calculation of cumulative delivered dose and delivered dose intensity, the actual dose administered at any visit will be derived as actual dose (mg) divided by BSA (m2) from the same visit. If BSA value from a visit is missing, it will be imputed as BSA from the previous visit. If BSA value from C1D1 is missing, it will be imputed as BSA from Screening Visit. If BSA from Screening Visit and C1D1 are both missing, BSA value at C1D1 will be imputed as 1.7 m2.

IV = intravenous. BSA = body surface area. C1D1 = Cycle 1 Day 1.

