#### 12.4.5. Study Drug Exposure, Modification and Dose Intensity

The summary described below will be based on the safety population.

Duration of study drug exposure will be defined for sacituzumab govitecan-hziy and for trilaciclib and summarized. The number of cycles that patients have received will be summarized by descriptive statistics as a continuous variable, while the number of cycles that are completed will be summarized as a categorical variable.

Study drug modifications will be summarized in three categories: sacituzumab govitecan-hziy dose reductions, sacituzumab govitecan-hziy cycle delay, and infusion interruption. The number and percentage of patients who have any sacituzumab govitecan-hziy dose reductions will be summarized; the number and percentage of patients who have at least one cycle delay will be summarized along with a summary of the number of cycles that have been delayed; the number and percentage of patients who have at least one infusion interruption for trilaciclib or sacituzumab govitecan-hziy will be summarized along with a summary of the number of interruptions. Lastly, the primary reason for each form of study drug modification (sacituzumab govitecan-hziy dose reductions, cycle delay, and infusion interruption) will also be summarized.

For trilaciclib and sacituzumab govitecan-hziy, cumulative dose, dose intensity, relative dose, and relative dose intensity will be derived and summarized.

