4.3. Definitions for Analysis Related Timepoint and Time Interval

Timepoint and time intervals related to efficacy and safety data collected during the treatment period will be summarized. For each specific category of data, the time interval by which the data will be analyzed or summarized will be specified in the respective section in which the data analysis plan is described.

To clarify data inclusion for each time interval of interest and baseline or end values for each given time interval, Table 3 presents definitions for timepoints, timepoint related assessments, and time intervals involved in statistical data analysis or summary.

Table 3Definitions for Timepoints, Timepoint Related Assessments and Time
Intervals

Term	Definition
Start of study (date)	Date of first dose of any study drug
Study baseline (assessment)	The last non-missing value prior to or on the date of the first dose of any study drug at the time that is before the time of the first study drug administration. If the event occurs on the same day as date of first dose of study drug but does not have the exact time captured, the event is assumed to have occurred prior to the first dose of study drug.
Day 1 of Cycle X (date)	The date when the first dose of any study drug for cycle X is administered. Day 1 of Cycle 1 (C1D1) is the same as the start of study.
End of a cycle (date)	It is defined as Day 1 of the subsequent cycle if the cycle is not the last cycle. For the last cycle, it is defined as the date of the End of Treatment Visit (ETV). If the ETV does not occur for a patient, End of the last cycle will be defined as 14 days post the last dose of any study drug.
Duration of a cycle (days)	Total number of days from Day 1 of the cycle to End of the cycle. That is, End of the cycle $-$ Day 1 of the cycle $+$ 1.
Duration of study drug exposure (weeks)	The total number of weeks from Day 1 of Cycle 1 to the End of the last cycle in the study. That is, (End of the last cycle –Day 1 of Cycle $1 + 1$) / 7.
Duration of total follow-up (months)	The total number of months from Day 1 of Cycle 1 to either the date of death or last contact date in the study known alive, inclusive. That is, duration of total follow-up=(date of death or date of last contact date known alive – Day 1 of Cycle $1 + 1$)/30.4375.

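### SAP Table 4: the sacituzumab govitecan relative dose intensity formula lacks inner brackets and, coded as printed, gives values 9 times too small

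*SAP*

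**What the plan says.** SAP section 7.2, Table 4, sets out the dose administration parameters for each drug. Its row for relative dose intensity gives the meaning as "Delivered dose intensity over prescribed dose intensity". The two formula cells in that row are:

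- trilaciclib: "Delivered dose intensity/(480/3)]*100"
- sacituzumab govitecan: "Delivered dose intensity/20/3]*100"

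The schedule row of the same table gives sacituzumab govitecan as "10 mg/kg IV administered on Day 1 and Day 8 of each 21-day cycle". The row for relative cumulative dose divides by 10 × 2 × the number of cycles, that is, 20 mg/kg per cycle.

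The variable is to be reported. Protocol section 12.4.5 says that for both drugs "cumulative dose, dose intensity, relative dose, and relative dose intensity will be derived and summarized", but gives no formula. SAP section 7.2 summarizes it as a continuous variable and adds: "All variables described in Table 4 will be included in the data listing except for the study drug administration schedule". SAP section 10 drops several items from the abbreviated report, but dose intensity is not among them.

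**The concern.** The sacituzumab govitecan cell has the same form as the trilaciclib cell except that the divisor has lost its brackets. Division is evaluated left to right, in SAS as elsewhere, so dividing by 20 and then by 3 is division by 60, whereas the row definition calls for division by 20/3.

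If the cell is transcribed literally, the summary table and the patient listing would show sacituzumab govitecan at roughly one ninth of its true relative dose intensity, beside a correct trilaciclib value for the same patients. Sacituzumab govitecan is also the drug for which the measure is the more informative: SAP Table 5 allows it two dose reductions and trilaciclib none, and protocol section 4.2.1 links the expected anti-tumor benefit partly to maintained chemotherapy dose intensity.

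**Working it through.** **Inputs**

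- Prescribed sacituzumab govitecan dose: 10 mg/kg on Days 1 and 8 of a 21-day cycle (SAP Table 4), so 20 mg/kg per 3 weeks.
- Prescribed trilaciclib dose: 240 mg/m² on the same days, so 480 mg/m² per 3 weeks.
- Delivered dose intensity: cumulative dose divided by weeks of exposure (SAP Table 4).
- Weeks of exposure: counted from the first dosing day to the close of the final cycle, both end days included, divided by 7 (SAP section 7.1). The last cycle ends at the End of Treatment Visit. If there is none, "End of the last cycle will be defined as 14 days post the last dose of any study drug" (SAP section 4.3, Table 3).

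The SAP gives a formula here and no numerical result, so the test is whether the formula returns what the row definition requires.

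**Size of the error**

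Prescribed intensity = 20/3 = 6.667 mg/kg/week. Printed divisor, left to right = 20 × 3 = 60. Ratio = 60 ÷ (20/3) = 9. The ratio contains no patient data, so it does not depend on cycles, delays or dose reductions.

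**Nominal dosing** (exactly 3 weeks per cycle)

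| Share of prescribed dose delivered | Delivered intensity (mg/kg/week) | As printed | With (20/3) |
|---|---|---|---|
| 100% | 6.667 | 11.1% | 100% |
| 75% | 5.000 | 8.3% | 75% |
| 50% | 3.333 | 5.6% | 50% |

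Control: trilaciclib at full dose is 160 mg/m²/week, and 160 ÷ (480/3) × 100 = 100%. The bracketed form behaves as defined.

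**Dosing under the SAP's own exposure rule**

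For n full cycles on schedule, with the last cycle ending 14 days after the last dose, exposure is 21(n − 1) + 7 + 14 + 1 = 21n + 1 days. Delivered intensity is 20n ÷ [(21n + 1)/7].

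| Cycles | Days | Delivered intensity (mg/kg/week) | As printed | With (20/3) | Trilaciclib, same patient |
|---|---|---|---|---|---|
| 1 | 22 | 6.364 | 10.6% | 95.5% | 95.5% |
| 6 | 127 | 6.614 | 11.0% | 99.2% | 99.2% |
| 12 | 253 | 6.640 | 11.1% | 99.6% | 99.6% |

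Relative cumulative dose for these patients is 20n ÷ (10 × 2 × n) × 100 = 100% throughout. The small shortfall below 100% in the bracketed column comes from counting both end days and is separate from the bracket error.

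**End of Treatment window**

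The visit may fall 7 days either side of day 14 after the last dose. For a single full cycle, exposure is then 15 to 29 days. The printed formula gives 15.6% down to 8.1%, and the bracketed formula 140% down to 72.4%. That spread belongs to the exposure rule and would occur with correct brackets. The ratio stays at 9.

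**The case against.** The strongest reply is that the table explains itself. The definition, the schedule, the per-cycle denominator in the row above and the bracketed trilaciclib cell all point to 20/3, so this is a typographical slip with one sensible reading. SAP section 1 also places separate programming documents between the SAP and the output, and the harm needs someone to transcribe the cell literally through all of them. If that happened, a ceiling near 11% beside a relative cumulative dose of 100% would be hard to miss, and delivered dose intensity is in the same listing, so a reader could recompute the value. Finally, the variable is descriptive: the dose-modification endpoints in SAP section 8.1.4 count reductions and delays and do not use it.

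All of this stands as far as it goes, and it limits the weight of the point. It does not make the printed formula right. The programming documents are to be developed from the SAP, and where SAP and protocol differ on methods the SAP prevails. A programmer who coded the cell exactly would therefore be following the plan and producing a wrong number, with no other formula in either document to set against it.

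One might also suspect that a pair of brackets was lost when the table was reproduced. That cannot be fully excluded, but the square brackets of this cell and the round brackets of its neighbour are intact, so it is unlikely.

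**Conclusion.** The formula is wrong as written. If it is coded as printed and evaluated left to right, each sacituzumab govitecan relative dose intensity is understated by a factor of exactly 9. The factor needs no assumption about the data. The tabulated percentages assume on-schedule dosing, and those under the SAP's exposure rule also assume an End of Treatment Visit at 14 days.

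The reach is narrow. Cumulative dose, delivered dose intensity, relative cumulative dose, all trilaciclib parameters and every efficacy and myeloprotection endpoint are unaffected. Whether the reported figures carry the error is unknown without the code. The point should be fixed because the output is required and the correction is trivial, but it does not threaten the trial's conclusions on efficacy.

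**What to change.** In SAP Table 4, print the sacituzumab govitecan cell as [Delivered dose intensity/(20/3)]\*100, in the same form as the trilaciclib cell. Then check the programming specification and code with one fully dosed test patient: one cycle, on schedule, End of Treatment Visit 14 days after the last dose. The program should return 95.5% for both drugs; a sacituzumab govitecan value of 10.6% means that the printed formula was coded. If exposure tables or listings have already been produced, make the same comparison on them.

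The cost is one pair of brackets in the SAP and a one-patient check of the program. No dose, schedule, endpoint or analysis population changes.
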